The Intensive PK sampling must be initiated on the same day (ideally in the morning) as the first dose of the study drug regimen, and conducted over the course of 72 hours according to the following time points: just prior to the first dose (t0), then 0.5h, 1h, 2h, 4h, 5h, 8h, 12h, 24h, 48h and 72h after the observed dose. Depending on site capacity, women may stay at the clinical research facility overnight after day 1 of the Entry Visit or return to the clinic at a designated time in the morning for administration of study drug and initiation of PK sampling. The same procedure can be followed for obtaining the PK samples at 48 and 72 hours after dosing.

Women will be asked to refrain from eating for two hours prior to each PK sampling dose of study drug, except for the meal provided by the site, which is to be eaten within 30 minutes before study drug administration. Women will be asked to refrain from further intake (except water) until three to four hours after the dose. The food type and quantity prior to each PK sampling dose will be recorded on CRFs.

RPT PK testing will be performed on all Intensive PK samples, after which, the t0 and 2h (or 4h) samples will be stored for later INH PK testing (see LPC for further details).

Women will be counseled about the signs and symptoms of active TB and asked to come to the clinic for an interim visit should any of the symptoms develop during the course of the study.

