6.3 Mother Weekly Visit (On Study Drug Regimen), Sparse PK Visit

Women will have weekly study visits while on the study drug regimen. Requirements for sequencing of procedures at the weekly visits are as follows:

- Before administering study drug regimen:
 - Prescribe study drug regimen per site SOP
 - Provide meal

The PK sampling visits are ideally conducted in the morning. The Sparse PK sample collection will be conducted on the visit of the woman's last dose of the study drug regimen over the course of 48 hours according to the following time points: 1h, 4h, 24h, and 48h after the observed dose. Women who are still taking study drug and breastfeeding postpartum will express breast milk, and plasma samples will also be drawn at the following time points:

- First weekly visit after delivery, three hours after the study drug dose
- Second weekly visit after delivery, six hours after the study drug dose
- Last dose visit, 24 hours after the study drug dose (breast milk collection only)

Women will be asked to refrain from eating for two hours prior to each PK sampling dose, except for the meal provided by the site, which is to be eaten within 30 minutes before study drug administration. Women will be asked to refrain from further intake (except water) until three to four hours after the dose. The food type and quantity prior to each PK sampling dose will be recorded on CRFs.

RPT PK testing will be performed on all Sparse PK samples, after which, the 1h and 4h samples will be stored for later INH PK testing (see LPC for further details).

Mother Weekly Visit Procedures (7 ± 2 days apart)		
Administrative and Regulatory		
 • Provide meal within 30 minutes prior to administering study drug
Behavioral and Counseling		
 • Signs and symptoms of active TB Counseling • Assess infant feeding methods (postpartum only)
Clinical		
 • Perform targeted physical exam • Record/update medical and medications history • Record/update AEs • Provide available test results • Assess TB symptoms, risk and exposure • Assess fetal movement and heart sounds (until delivery)

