10.5 Primary and Secondary Data Analysis Plan

Primary: Pharmacokinetic data (concentration-time data) and safety data of rifapentine and desacetyl-rifapentine in pregnant women; safety outcomes in infants

Secondary: Pharmacokinetic data of rifapentine and desacetyl-rifapentine in postpartum women and infants; pharmacokinetic data of isoniazid in pregnant and postpartum women

Population-based estimates of RPT CL/F, absorption, and volume of distribution will be derived for pregnant women in second and third trimesters of pregnancy and in the postpartum period. Study data will provide a mix of longitudinal and cross-sectional observations, which will be combined using standard algorithms in wide use in pharmacology research. The pharmacokinetics of the desacetyl-rifapentine (des-RPT) metabolite of RPT and INH will be estimated based on the sample in like fashion. Rates of adverse events and other safety-related parameters will be computed and reported for study monitoring and regulatory use. Secondary objectives are: characterization of PK data of RPT and des-RPT in the postpartum period, description of adverse and safety outcomes in pregnant women, assessment of impact of covariates on primary PK parameters, comparison of RPT and des-RPT exposures between study participants and non-pregnant historical controls, estimation of effective RPT dose for pregnant women, estimation of RPT concentrations in newborns, description of pregnancy and infant safety outcomes, description of RPT + INH tolerability in pregnancy, and characterization of PK data of INH in pregnant and postpartum women.

The primary tool for estimation of parameters of interest is the single compartment model for RPT absorption and disposition kinetics:

$$\frac{dA(1)}{dt} = -ka \times A(1); \text{ Absorption compartment}$$
$$\frac{dA(2)}{dt} = ka \times A(1) - \frac{CL}{V} \times A(2); \text{ Central Plasma compartment}$$

The parameters CL and V will be elaborated upon to incorporate allometric scaling and effects of gestational age.

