Secondary PK parameters for RPT and des-RPT (area under the curve (AUC), maximum concentration (C_{max}), and minimum concentration (C_{min})) will be derived from the model for pregnant women in the second and third trimesters of pregnancy.

P2001 PHARMACOKINETIC ANALYSIS PLAN

The study data, which provide a mix of longitudinal and cross-sectional observations, will be combined and modeled using nonlinear mixed effects approaches that are widely used in pharmacology research. Nonlinear mixed effects modeling will be performed using NONMEM v7.4. Dataset manipulation and data visualization will be performed using R v3.5.1 and Microsoft Office Excel. Perl-speaks-NONMEM (PsN) v4.8.1 and Xpose4 v4.6.1 will be used for model evaluation.

Exploratory data analysis

Prior to beginning modeling analyses, the following exploratory data analyses will be performed:

- Scatterplots of dependent variable (DV) versus time, stratified by treatment outcome, cohort, or disease status
- Summary statistics including the number of patients, samples, samples per patient, and number of patients with samples at each visit.

Structural model development

The absorption and disposition kinetics of RPT and des-PRT will be described by a one compartment model with first-order (linear) elimination and first-order oral absorption. More complex models with respect to absorption (e.g. transit compartments), distribution, and elimination will be explored if necessary.

Goodness-of-fit diagnostic plots will be used to assess the structural model:

- Observations versus population and individual predictions
- Population, individual, and conditional weighted residuals versus time

Stochastic model development

Exponential error models will be used to characterize the between-subject-variability of the model parameters. A diagonal sigma-structure will be used, and off-diagonal elements may be included.

For continuous data, additive, proportional, and combined (additive and proportional) error models will be used to characterize the residual variability.

The appropriateness of the random error models will be assessed using diagnostic plots:

- Observations versus population and individual predictions
- Population, individual, and conditional weighted residuals versus time
- Observations versus time with population and individual fits
- Histogram of ETA estimates

Model evaluation

Visual predictive checks will be used to evaluate how well the model describes the data.

Infants

Approach

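### The SAP's rifapentine model has no inter-occasion variability, so if clearance or bioavailability varies between visits, model-based intervals for within-woman stage contrasts will be too narrow

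*SAP*

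**What the plan says.** The SAP pools all maternal RPT data in one model: "The study data, which provide a mix of longitudinal and cross-sectional observations, will be combined and modeled using nonlinear mixed effects approaches". Protocol 10.5 describes the data in the same way. Under Stochastic model development (RPT and des-RPT, Adults), the SAP gives two layers of variability:

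- Between women: "Exponential error models will be used to characterize the between-subject-variability of the model parameters".
- Residual: "additive, proportional, and combined (additive and proportional) error models will be used to characterize the residual variability".

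It adds: "A diagonal sigma-structure will be used, and off-diagonal elements may be included". Off-diagonal terms are covariances between random effects; they do not create an occasion level. The SAP's allowance for more complex models covers absorption, distribution and elimination, not the random effects. Neither the SAP nor Protocol section 10 mentions IOV, and Appendix II reports inter-patient variability only.

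The sampling is at least two-occasion by design:

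- Entry visit (Protocol 6.2): "just prior to the first dose (t0), then 0.5h, 1h, 2h, 4h, 5h, 8h, 12h, 24h, 48h and 72h after the observed dose".
- Last dose (Protocol 6.3): "The Sparse PK sample collection will be conducted on the visit of the woman's last dose of the study drug regimen", with samples "over the course of 48 hours according to the following time points: 1h, 4h, 24h, and 48h after the observed dose".
- Women who breastfeed while still on study drug also give plasma at 3 h and 6 h after dosing, at their first and second weekly postpartum visits (Protocol 6.3).

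**The concern.** A woman's apparent clearance on one day is not exactly her clearance 11 weeks later, even if pregnancy stage has no effect. Meal, absorption and intercurrent illness all move it. A model with only a woman-level effect and independent residuals has nowhere to put such a shift. It treats the four last-dose samples as four independent pieces of evidence about the stage effect, although they share one occasion's shift. The point estimate then carries more noise than the model reports.

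The contrast matters here. Protocol 9.1 makes maintenance of drug levels between the second and third trimesters the central question. Objective 2.1.1 asks for PK in both trimesters, 2.2.1 for postpartum PK and 2.2.2 for the gestational-age effect. Protocol 9.5.1 justifies the sample size partly by the precision of the trimester contrast in clearance. An interval that is too narrow could present ordinary visit-to-visit variation as an effect of pregnancy or delivery.

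**Working it through.** **The plan's own figure.** Table 3 gives an RSE of 18% for the trimester contrast at N = 50. It cannot be rebuilt, because the effect size, residual error, sampling split and any IOV used are not stated. It is internally coherent: RSE × √N stays between about 117 and 132 at every N, and the power follows from Φ(1/0.18 − 1.96) = Φ(3.60) = 99.98%, against 99.9% stated.

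**Inputs from the documents.**
- 25 women per cohort; 10 post-dose samples at the first dose and 4 at the last.
- Interval: dose 1 to dose 12 is 11 weeks on a weekly schedule.
- CL/F 1.47 L/h (60 kg, fed; Protocol 10.3.2).
- V/F = 51.7 × (60/70) / 1.40 = 31.7 L (Appendix II).
- Between-subject variability 40% on CL/F and 47% on V/F (Appendix II).

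**Assumptions not in the documents.** Residual error 15%, 25% or 35% (20% or 35% in the simulations); variability of ka between women 50%; IOV up to 30%; no dropout.

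**Step 1: within-woman information dominates.** With 40% variability, a between-woman comparison of 25 against 25 has SE of at least 0.40 × √(2/25) = 0.113 on log CL/F. The within-woman contrast in 25 women, with no IOV, has SE 0.014, 0.024 and 0.033 at residual error 15%, 25% and 35%. A pooled model therefore leans on the within-woman part.

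**Step 2: what IOV adds.** Each woman's difference carries two independent occasion shifts, so

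true SE² ≈ SE₀² + 2 × IOV² / 25.

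At 25% residual error and 10% IOV: √(0.024² + 2 × 0.10²/25) = √(0.000576 + 0.0008) = 0.037. At 20% IOV: √(0.000576 + 0.0032) = 0.061.

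**Step 3: what the model without IOV reports.** Its variances are set to their best fit to data that contain IOV. Coverage of a nominal 95% interval is 2Φ(1.96/ratio) − 1. Results for IOV on CL/F, linearised one-compartment model, 25 women (ratios from unrounded SEs):

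| Residual error | IOV | True SE | Reported SE | Ratio | Coverage |
|---|---|---|---|---|---|
| 15% | 10% | 0.032 | 0.017 | 1.91 | 70% |
| 15% | 20% | 0.058 | 0.022 | 2.63 | 54% |
| 25% | 10% | 0.037 | 0.025 | 1.46 | 82% |
| 25% | 20% | 0.061 | 0.029 | 2.10 | 65% |
| 35% | 10% | 0.044 | 0.034 | 1.27 | 88% |
| 35% | 20% | 0.066 | 0.037 | 1.76 | 74% |

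With both cohorts in one model the ratios are nearly the same. With IOV of 10-30% in bioavailability and 30% in ka, instead of in CL/F, the ratio runs from 1.07 to 1.92. With no IOV it is 1.00.

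**Step 4: full nonlinear fits.** Two sets of FOCE-type simulations used 25 women, the planned times and no true stage effect (200 and 100 replicates per setting at 20% residual error).
- At IOV of 5/10/20%, SD/SE was 1.9/3.1/6.0 in one set and 1.9/3.1/4.8 in the other. The nominal 5% test rejected in 28/57/72% and 29/51/69% of trials.
- At 35% residual error and IOV of 10/20%, it rejected in 35/61% and 36/59%.
- With IOV in the model, rejection was 6-9%.

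**Step 5: link to Table 3.** Suppose its 18% excluded IOV, the effect is 25% and all 50 women contribute within-woman. The implied SE is 0.18 × 0.25 = 0.045. Adding 2 × IOV²/50 gives √(0.045² + 0.02²)/0.25 = 19.7% at 10% IOV and √(0.045² + 0.04²)/0.25 = 24.1% at 20%. Power stays at 99.9% and 98.6%. On this reading precision worsens by a factor of 1.09 to 1.34, and planned power is not the problem.

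**The case against.** **The harm depends on outputs the SAP does not specify.** It names no stage test, confidence interval or SE method, and the objective is estimation. This stands as a limit on the claim. A participant-level bootstrap or sandwich SE would remove much of the understatement, though perhaps not all: in simulation a sandwich SE still rejected 10-17% at IOV of 5-20%. The estimate itself was also noisier without IOV (SD 0.100 against 0.057 at 20% IOV and 20% residual error).

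**The size is unknown, and the largest figures are idealised.** This also stands. The simulations use log-scale error with no assay limit, so very low late concentrations count as fully precise. In a linearised check with variances held at their true values, an illustrative limit of 0.05 mg/L cut the ratio from 3.7 to 2.6 at 10% IOV and from 8.0 to 5.2 at 20%.

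**A spurious effect would usually be modest.** In that check the contrast's true SD on log CL/F was about 0.04-0.05 at 10% IOV and 0.08-0.11 at 20%, against log 1.25 = 0.22 for the protocol's 25% criterion. That criterion concerns the comparison with historical controls, but the scale is a fair reminder.

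**Stronger readings a reader might infer, which the documents do not support:**
- *The interim dose decision is distorted.* It uses first-dose data only (Protocol 10.3), one occasion per woman. The first-dose comparison of Cohort 1 with Cohort 2 is between women. Neither is affected in this way.
- *Every woman changes stage.* On a weekly schedule, one enrolled before 17 weeks takes dose 12 before 17 + 11 = 28 weeks. One enrolled at 28 weeks reaches it at 39 weeks, possibly before delivery. Such women give no within-woman stage contrast. Evaluability does not require both profiles either.
- *The INH model has the same defect.* The SAP estimates INH irrespective of trimester or postpartum status, so there is no INH stage contrast to protect. The stored INH samples are pre-dose plus 2 h (or 4 h) at entry, then 1 h and 4 h at the last dose: too few per occasion to support IOV.

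**Conclusion.** The point holds in conditional form, for RPT and desRPT only. As written, the model understates model-based uncertainty for within-woman trimester and postpartum contrasts whenever IOV is not zero. The direction is clear; the size is not. For assumed IOV of 10-20% on CL/F and residual error of 15-35%, the linearised understatement is about 1.3- to 2.6-fold. Full simulations at 20% residual error give about 3-fold or more. If IOV lies in bioavailability and ka, the ratio is about 1.1 to 1.9. A reader might conclude that the standard errors will be far too small in any case. The documents do not support that, because they give no IOV, no residual error and no SE method. This is a worthwhile, inexpensive improvement to the analysis of a central contrast, not a fault that invalidates the plan.

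**What to change.** In the SAP, under Stochastic model development for RPT and des-RPT:

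1. Define the occasions: first dose, last dose and, where collected, each postpartum plasma visit.
2. Estimate IOV on CL/F, and test it on F and ka.
3. Report the trimester and postpartum contrasts, with their intervals, from the model that includes any supported IOV.
4. Give a participant-level bootstrap or robust interval as a check.

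No new data are needed. The cost is some SAP wording, one or more extra variance terms, and wider reported intervals for the stage contrasts if IOV is present. If it is negligible, little is lost: in simulation with essentially no IOV, the median SE was 0.014 with the term and 0.013 without it. No change is needed for INH.

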2.2 Secondary Objectives

- 2.2.1 To estimate the population pharmacokinetics (PK) (CL/F, absorption, volume of distribution) of RPT and its desacetyl-rifapentine metabolite (desRPT) among pregnant women during the postpartum period who are receiving once-weekly RPT (900mg or the new study dose, if a dose adjustment is indicated by the interim analysis) and once-weekly INH (900mg).
- 2.2.2 To assess the impact of covariates (gestational age, weight, age, HIV status) on primary PK parameters using population PK modeling.
- 2.2.3 To compare RPT and desRPT exposure pharmacokinetic parameters (AUC, C_{max} , C_{min}) for RPT in pregnant and postpartum women versus non-pregnant historical controls, using noncompartmental analyses.
- 2.2.4 To determine the RPT dose in pregnancy that achieves similar estimated exposure (AUC) of RPT as non-pregnant adults at standard doses.

- 2.2.5 To quantify RPT and desRPT concentrations at delivery among infants born to women receiving once-weekly RPT + INH.
- 2.2.6 To describe the tolerability of RPT + INH dosed once weekly for 12 weeks in pregnant and postpartum women.
- 2.2.7 To assess incidence of active TB in mother-infant pairs up to 24 weeks postpartum.
- 2.2.8 To explore the population pharmacokinetics (PK) (CL/F, absorption, volume of distribution) of INH in HIV-1-infected and HIV-1-uninfected pregnant and postpartum women (i.e., women who are and are not taking efavirenz (EFV)) who are receiving once-weekly RPT (900mg or the new study dose, if a dose adjustment is indicated by the interim analysis) and once-weekly INH (900mg).

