IMPAACT 2001

Final Pharmacokinetic Statistical Analysis Plan

**A Phase I/II Trial of the Pharmacokinetics, Tolerability, and Safety of Once-Weekly Rifapentine and Isoniazid in HIV-1-infected and HIV-1-uninfected Pregnant and Postpartum Women with Latent Tuberculosis Infection
Protocol Version 1.0**

ClinicalTrials.gov Identifier: NCT02651259

P2001 PHARMACOKINETIC ANALYSIS PLAN

OBJECTIVES

Primary

Pharmacokinetic (PK, concentration-time) data and safety data of rifapentine (RPT) and desacetyl-rifapentine (des-RPT, metabolite) in pregnant women

Secondary

PK data of RPT and des-RPT in postpartum women and infants; PK data of isoniazid (INH) in pregnant and postpartum women

DATA

Dataset checking

Source datasets provided to UCSF will be checked by IMPAACT against the original database. Datasets may need to be subsequently manipulated during the PK analysis. Each time manipulations are performed the new dataset will be checked against the original dataset. The following checks will be performed:

- Comparison of number of subjects in the new dataset to those expected to be retained from the initial dataset
- Number of observations per subject in the new dataset to those expected to be retained from the initial dataset
- Check of dosing history (PK sampling times relative to dosing, missing dosing or sampling times).

Any discrepancies/errors found in the dataset will be corrected and documented.

Exclusion of data points

All evaluable data will be used for analysis. All data exclusions will be documented.

Identification of outliers

Individual data points that are clearly aberrant and/or with residuals (weighted, conditional weighted, and/or individual weighted) greater than 6 will be considered for omission. An assessment of their impact on the analysis will be documented.

Handling of missing data

The population median value at each time point may be used for missing data from a continuous variable (e.g. age, weight, and serum creatinine level) for a particular subject. If any value is missing at baseline, screening values may be used for imputation, if available.

METHODOLOGY

RPT and des-RPT

Adults

Approach

Population-based estimates of PK parameters for RPT (CL/F, absorption, volume of distribution) and des-RPT (CL_{metabolite}/F) will be derived for

- (1) pregnant women in the second and third trimesters of pregnancy and
- (2) women after delivery (postpartum).

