Summary statistics will be compiled for plasma and cord blood RPT and des-RPT concentrations in infants collected within 72 hours following birth.

Dataset manipulation and data visualization will be performed using R v3.5.1 and Microsoft Office Excel.

Summary statistics

P2001 PHARMACOKINETIC ANALYSIS PLAN

Cord blood and plasma concentration data for RPT and des-RPT will be summarized by

- Count
- Minimum concentration and maximum concentration
- Mean and median
- First quantile and third quantile.

INH

Adults: Approach

Population-based estimates of PK parameters for INH (CL/F, absorption, volume of distribution) will be derived for all pregnant women irrespective of pregnancy trimester or pre-/post-partum status.

The study data, which provide a mix of longitudinal and cross-sectional observations, will be combined and modeled using nonlinear mixed effects approaches that are widely used in pharmacology research. Nonlinear mixed effects modeling will be performed using NONMEM v7.4. Dataset manipulation and data visualization will be performed using R v3.5.1 and Microsoft Office Excel. Perl-speaks-NONMEM (PsN) v4.8.1 and Xpose4 v4.6.1 will be used for model evaluation.

Exploratory data analysis

Prior to beginning modeling analyses, the following exploratory data analyses will be performed:

- Scatterplots of dependent variable (DV) versus time, stratified by treatment outcome, cohort, or disease status
- Summary statistics including the number of patients, samples, samples per patient, and number of patients with samples at each visit.

Structural model development

The absorption and disposition kinetics of INH will be described by a one compartment model with first-order (linear) elimination and first-order oral absorption. More complex models with respect to absorption, distribution, and elimination (e.g. mixture models) will be evaluated if necessary.

Goodness-of-fit diagnostic plots will be used to assess the structural model:

- Observations versus population and individual predictions
- Population, individual, and conditional weighted residuals versus time

Stochastic model development

Exponential error models will be used to characterize the between-subject-variability of the model parameters. A diagonal sigma-structure will be used, and off-diagonal elements may be included.

For continuous data, additive, proportional, and combined (additive and proportional) error models will be used to characterize the residual variability.

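### The SAP pools isoniazid PK over pregnancy stage and gives no HIV/efavirenz estimate, so the groups named in exploratory objective 2.2.8 get no parameter estimate

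*SAP*

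**What the plan says.** Protocol objective 2.2.8 is secondary: "To explore the population pharmacokinetics (PK) (CL/F, absorption, volume of distribution) of INH" in women with and without HIV, both pregnant and postpartum. It explains the HIV grouping as "i.e., women who are and are not taking efavirenz (EFV"). The matching outcome measure, 9.2.2.6, asks for INH estimates and mentions no subgroup.

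Protocol section 10.5 plans rifapentine estimates for the second trimester, the third trimester and postpartum. It then says that INH will be estimated in the same manner.

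The SAP lists its INH objective as "PK data of isoniazid (INH) in pregnant and postpartum women", without HIV or EFV. Under INH, Adults: Approach, it derives the parameters for all the women together, "irrespective of pregnancy trimester or pre-/post-partum status". Exploratory plots are "stratified by treatment outcome, cohort, or disease status". The only model extension offered is: "More complex models with respect to absorption, distribution, and elimination (e.g. mixture models) will be evaluated if necessary". The INH section names no covariate.

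**The concern.** The SAP does more than leave detail out. It states a pooling rule for INH that departs from protocol 10.5, and it gives no reason. For rifapentine, the same SAP separates pregnant from postpartum women, so the pooling is particular to INH.

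A model fitted as written would report one typical clearance over a mixture of pregnancy stages and of EFV users and non-users. A difference between the HIV/EFV groups would be absorbed into between-subject variance. A change from pregnancy to postpartum often happens within a woman, between her first and last dose, so part of it would fall into residual error. In neither case would a reader see the groups that the objective names. If the groups were compared only after the pooled fit, the comparison would not be pre-specified.

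**Working it through.** **Text check**

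| Element of objective 2.2.8 | Where the SAP covers it for INH |
|---|---|
| Clearance, absorption, volume | Yes, pooled |
| Pregnant versus postpartum | Pooled by explicit rule |
| HIV-infected (on EFV) versus uninfected (not on EFV) | No model term, no by-group estimate |

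Three items might fill the gaps.
- *The scatterplots.* They show concentrations and estimate no PK parameter. The disease-status label is undefined and is one of three alternatives. Cohort is gestational stage at entry, not pregnant versus postpartum.
- *The mixture models.* These look for latent subgroups, not the observed HIV/EFV groups, and are conditional on need.
- *Objective 2.2.2.* It lists HIV status and gestational age as covariates, but for the primary PK parameters. Under objective 2.1.1 those are rifapentine and its metabolite.

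**What the data can support**

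- *HIV and EFV.* Protocol 4.1.5 requires every HIV-infected woman to enter on EFV plus two NRTIs. HIV, EFV and NRTI use therefore coincide at entry, and only one combined contrast is estimable.
- *Numbers.* Protocol 9.4 targets at least 10 evaluable HIV-infected women per cohort, so at least 2 × 10 = 20 of 50, leaving at most 30 uninfected.
- *Samples.* INH is to be assayed at t0 and at 2h or 4h around the first dose (protocol 6.2), and at 1h and 4h after the last dose (6.3). The t0 sample precedes any study INH and says nothing about clearance. That leaves 1 + 2 = 3 informative samples per woman.
- *Stage.* Entry samples are always antenatal and first-dose. Postpartum INH samples come from the last dose. With 12 weekly doses on schedule, the last falls 11 weeks after the first: at 28 + 11 = 39 to 34 + 11 = 45 weeks counted from conception dating for Cohort 2, and at 25 to under 39 weeks for Cohort 1. Many Cohort 2 last doses should therefore be postpartum and most Cohort 1 last doses antenatal. Stage is partly confounded with dosing occasion and is separable mainly through women still pregnant at their last dose.

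**Illustrative precision of the HIV/EFV ratio**

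The documents give no INH variability, power or precision, so there is no figure to reproduce. Assume 20 versus 30 women, lognormal CL/F, and each woman's CL/F known without error.

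Log-scale SD: s = √ln(1 + CV²). SE of the log ratio = s × √(1/20 + 1/30) = s × 0.2887. The 95% CI multiplies and divides the ratio by exp(1.96 × SE).

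| Assumed CV | s | SE | CI factor |
|---|---|---|---|
| 30% | 0.294 | 0.0847 | 1.18 |
| 50% | 0.472 | 0.136 | 1.31 |
| 70% | 0.631 | 0.182 | 1.43 |

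A 25/25 split gives 1.18, 1.30 and 1.42. With three informative samples per woman the real intervals will be wider. No interval is given for pregnant versus postpartum, because the documents do not say how many women will have delivered before their last dose.

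**The case against.** The strongest reply is that the objective only explores. It names no contrast, ratio or test, and its HIV/EFV wording can be read as describing who is included. Outcome 9.2.2.6 asks for INH estimates without subgroups, and the SAP supplies them. A reader might infer that objective 2.2.8 goes unanswered; the documents do not support that. The reply does not fully dispose of the point. Exploring removes the need for a test, but the objective still names its groups, and protocol 10.5 still ties the INH analysis to the staged rifapentine analysis.

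It is also fair that the HIV/EFV half is not peculiar to INH. Protocol 10.5 describes the INH analysis by pregnant and postpartum women only, and the SAP's rifapentine section has no covariate model either. That makes the gap wider without closing it for INH.

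Sparse sampling may well explain the pooling, and pooling could be defended on that ground. The SAP does not say so. Thin data justify wide intervals or a stated limitation.

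Finally, a reader might take the illustrative intervals to mean that the trial could detect an EFV interaction with INH. They do not show that: they are a best case on assumed variability, HIV and EFV cannot be separated, and the documents give no reason to expect EFV to alter INH. The background in protocol 1.2 describes INH raising EFV concentrations in some women.

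**Conclusion.** The point holds in a limited form. The SAP's INH pooling rule departs from protocol 10.5, and no planned parameter estimate addresses the HIV/EFV or the pregnant-versus-postpartum part of objective 2.2.8. The pooled INH estimates will be delivered. The consequence is confined to an exploratory secondary objective; the interim dose rule in protocol 10.3 uses rifapentine clearance only.

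This conclusion rests on the text and on no numerical assumption. The precision figures (a factor of about 1.18 to 1.43, and 1.31 at a CV of 50%) show only that a combined HIV/EFV ratio could be reported as an imprecise estimate. They depend on the assumed 20:30 split, the assumed CV and the optimistic treatment of individual clearance as known.

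**What to change.** In the SAP's INH section:
- Keep the pooled estimates as a summary.
- Add HIV/EFV status and pregnant versus postpartum status as pre-specified exploratory covariates on INH CL/F. Report each as a ratio with a 95% CI and no test.
- State that HIV/EFV is one combined contrast, because all HIV-infected women enter on EFV plus two NRTIs.
- State that stage is partly confounded with dosing occasion, and why.
- Define disease status in the plot specification.

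If the modelling group judges that the data cannot support these terms, the SAP should give its reason for pooling, and objective 2.2.8 should be narrowed to match.

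The cost is SAP text and some extra model fitting, with no new samples or participants. The drawback is wide intervals, and possibly an unstable stage term if few women are still pregnant, or few have delivered, at the last dose.
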